8.4.4. Safety and Tolerability Analyses

The Safety Population will be used for all safety assessments. All safety assessments will be descriptive and no inferential statistics are planned for safety assessments. All data listings will be provided for protocol specified safety data.

8.4.4.1. Adverse Events

The Medical Dictionary for Regulatory Activities (MedDRA, version 20.0) will be used to classify all AEs. Adverse event summaries will include only treatment-emergent AEs (TEAEs) by treatment group. Treatment-emergent adverse events (TEAEs) are defined as AEs that first occurred or worsened during the indicated treatment phase.

The number and percentage of patients with TEAEs will be summarized by system organ class (SOC) and preferred term (PT). Summaries of AEs by severity and relationship to the study treatment will also be provided. Serious adverse events (SAEs) and AEs resulting in discontinuation will be summarized separately in a similar manner. Patient listings of AEs and SAEs will be produced.

8.4.4.2. Clinical Laboratory Evaluations

For the continuous laboratory parameters, descriptive statistics will be presented for values collected at Screening, Initial and Extended Treatment, and End of Study/Early Withdrawal Visits, and for the changes from baseline to End of Study/Early Withdrawal.

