Assessment of current AETs	X					X	X	X	X	X	X	X
Medical/surgical history	X											
Seizure History ^d	X											
Concomitant medications	X	X	X	X	X	X	X	X	X	X	X	X
Vital Signs ^e	X	X	X	X	X	X	X	X	X	X		
Clinical Labs	X		X	X		X	X	X	X	X		
Physical Exam	X											
Height/Weight	X		X	X	X	X	X	X	X	X		
Head Circumference	X					X			X	X		

	SCREENING PERIOD	INITIAL TREATMENT PERIOD					EXTENDED TREATMENT PERIOD				Taper Period	Follow-up Period
Visit	1	2	3	4	5	6	7	8	9	Early Withdrawal ^m	6 days	30 days
Day	-14 to -1	Titration Days 1	Titration Day 4	Day 7	Day 14 ^a	Day 15 EOS ^b (+ 5 days)	Week 6	Week 10	Week 13 EOS ^b			
Neurological Exam ^f	X	X	X	X	X	X	X	X	X	X		
Study Drug Dosing		X ^g	X ^h	X ^h	X ^h	X ⁱ	X ⁱ	X ⁱ	X ⁱ	X ⁱ	X ^j	
Assess AEs		X	X	X	X	X	X	X	X	X	X	X
PK blood sampling ^k						X						
Investigator CGI-S	X											
Investigator CGI-I						X				X		
Seizure Diary ^l	X	X	X	X	X	X	X	X	X	X	X	
Meal Diary ⁿ					X	X						

Abbreviations: AE = adverse event; AETs = antiepileptic therapies; CGI-I = Clinical Global Impression-Global Improvement Scale; CGI-S = Clinical Global Impression-Severity; EEG = electroencephalography; EOS = End of Study; ICF = informed consent form; PK = pharmacokinetic.

^a Patients will be admitted to the study center as an inpatient on Day 14 and discharged on Day 15 following the completion of End of Study assessments.

^b End of Study assessments will be completed at Day 15 for partial and non-responder patients and Week 13 for patients who complete the extension period of the study.

^c Patients will have a minimum of a 9-hour video EEG that includes at least one full sleep-wake cycle during their Screening Visit and a 24-hour video EEG at Visit 5 (Day 14 to Day 15) during the Initial Treatment Period. A minimum of 9-hour video-EEG will be performed during the Extended Treatment Period to

confirm parent/caregiver report of relapse or complete resolution or at Early Withdrawal for patients who have continued into the Extended Treatment Period. A Video EEG is not required for patients who decide to withdraw during the Initial Treatment Period

^d To assess preliminary efficacy, a seizure history will be collected at screening to record the approximate number of seizures in the last 28 days as reported by the parent/caregiver.

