3.1.2. Extended Treatment Period

Following the Initial Treatment Period:

- Complete Responders will continue receiving their assigned treatments of vigabatrin plus either CBD 40 mg/kg/day or placebo for 75 days, until Week 13 (Day 90), to monitor progress for treatment response.
- During the Extended Treatment Period, the investigator may reduce the dose of CBD or CBD placebo to 30 mg/kg/day for safety or tolerability. If the subjects cannot tolerate the 30 mg/kg/day, the drug will be discontinued and the patient withdrawn from the study following the completion of the taper period.

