7.2.5. Early Withdrawal Visit

Should a patient's participation be terminated prior to Day 14 or Day 90 for any reason (see [Section 3.3](#)), an Early Withdrawal Visit will be completed. The following procedures will be completed:

- Record concomitant medications and AETs.
- Record vital signs (seated or supine blood pressure ([depending on patient age and ability]), pulse rate, respiratory rate, and temperature measurements).
- Record height and weight and head circumference.
- Record and review daily seizure diary.
- Perform a complete neurological examination (see [Section 6.2.3](#)).
- Complete investigator CGI-I.
- Record AEs.
- Perform 9-hour video EEG, if possible only for patients that continued into the Extended Treatment Period.
- Draw blood samples for hematology and chemistry.
 - [Section 7.4](#) details the volume of samples to be drawn based on patient age.

All patients will begin tapering off investigational product and vigabatrin at this visit (see [Section 7.2.2](#)).

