8.4.1. Study Patients and Demographics

8.4.1.1. Disposition and Withdrawals

The numbers of patients randomized, completing, and withdrawing, along with reasons for withdrawal, will be tabulated overall and by treatment group. The number of patients in each analysis population will be reported.

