8.4.4.3. Vital Signs

For blood pressure, pulse rate, temperature, and respiration rate, descriptive statistics will be presented for values collected at Screening, Initial and Extended Treatment, End of Study /Early Withdrawal, and Follow-up Visits, and for the changes from baseline to End of Study /Early Withdrawal.

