#### 6.3.1. Visit Windows Relative to the First Dose of Study Medication

**Table 2: Visit windows and target days**

Visit	Relative Target Day	Visit Window
Visit 1 (Screening)	-14	-14 – -1
Visit 2	Day 1	1
Visit 3	4	4
Visit 4	13	13
Visit 5 (End of Study)	14	14
Visit 6	Week 6	
Visit 7	Week 10	
Visit 8 (End of Study)	Week 13	
Early Withdrawal		
Taper Period		3 days
Followup Period		30 days

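### The protocol's End of Study change for laboratory values and vital signs, and its single disposition table, depend on response, because End of Study is Day 15 or Week 13

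*Protocol*

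**What the plan says.** **Change summaries.** Protocol 8.4.4.2 presents laboratory values at screening and at the treatment-period and end visits, "and for the changes from baseline to End of Study/Early Withdrawal". Protocol 8.4.4.3 does the same for vital signs: "and for the changes from baseline to End of Study /Early Withdrawal". Neither section names a visit.

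**When End of Study is.** Footnote b of Table 1 (Schedule of Events) reads: "End of Study assessments will be completed at Day 15 for partial and non-responder patients and Week 13 for patients who complete the extension". Under Protocol 3.1.2 only complete responders continue, "for 75 days, until Week 13 (Day 90), to monitor progress for treatment response".

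**Disposition.** Protocol 8.4.1.1 states: "The numbers of patients randomized, completing, and withdrawing, along with reasons for withdrawal, will be tabulated overall and by treatment group". It does not define completion for each period. Protocol 7.2.5 sets two thresholds for early withdrawal ("Should a patient's participation be terminated prior to Day 14 or Day 90 for any reason") but does not link them to the disposition table. SAP 8.1.1 counts discontinuations and their reasons by treatment group without separating the periods, and SAP 11.10 lists completion status patient by patient.

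**By-visit summaries.** SAP 11.5 and 11.6 plan observed values and change from baseline at each visit. SAP 14.2 lists chemistry and vital-sign change tables by treatment group and study time. SAP Table 2 labels two visits as End of Study: Visit 5 (Day 14) and Visit 8 (Week 13).

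**The concern.** A change from baseline to End of Study is comparable between arms only if End of Study falls at the same time in both. Here the Day 15 response, which is the primary outcome, decides whether an infant's last value comes from Day 15 or Week 13. If CBD raises the response rate, the CBD summary contains more late values than the placebo summary. Any change in a laboratory value or vital sign that comes simply with time or age between the two visits would then look like a treatment effect. Early Withdrawal values add a third, unfixed time to the same row.

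The disposition table has a similar problem. A non-responder reaches the end at Day 15, while a complete responder has to stay a further 75 days. The arm with more responders therefore has more time at risk of withdrawal and may look less well tolerated for that reason alone.

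**Working it through.** The plan gives no figure for this point, so there is nothing to reproduce. The size follows from the plan's own inputs.

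**Inputs**
- Complete response 60% (CBD) and 40% (placebo); arm sizes 130 and 60: Protocol 8.2.
- End of Study at Day 15, or at Week 13 (Day 90): Table 1 footnote b and Protocol 3.1.2.
- Withdrawal risks: not in the documents. Assumed equal in both arms, at 5% by Day 15 and then 15% to 30% of complete responders during the extension.

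**Step 1. Mix of times, before any withdrawal**
- CBD: 130 × 0.6 = 78 values at Week 13 and 52 at Day 15.
- Placebo: 60 × 0.4 = 24 values at Week 13 and 36 at Day 15.

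**Step 2. Mean End of Study day** = p × 90 + (1 − p) × 15
- CBD: 0.6 × 90 + 0.4 × 15 = 60.
- Placebo: 0.4 × 90 + 0.6 × 15 = 45.
- Gap = 75 × (0.6 − 0.4) = 15 days.

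| Response, CBD v placebo | Mean day, CBD | Mean day, placebo |
|---|---|---|
| 60% v 40% (planned) | 60 | 45 |
| 50% v 30% | 52.5 | 37.5 |
| 70% v 50% | 67.5 | 52.5 |
| 40% v 40% | 45 | 45 |

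**Step 3. Effect of a shared drift.** Suppose a measurement changes by d between Day 15 and Week 13, identically in both arms and unrelated to treatment. The pooled summary carries 0.6d in the CBD arm and 0.4d in the placebo arm, a false difference of 0.6d − 0.4d = 0.2d.

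**Step 4. Disposition with equal risk in both arms.** Share withdrawn = 0.05 + p × w, where w is the risk in the extension.
- w = 15%: CBD 130 × 0.05 + 78 × 0.15 = 18.2, or 14.0%; placebo 60 × 0.05 + 24 × 0.15 = 6.6, or 11.0%.
- w = 30%: CBD 6.5 + 23.4 = 29.9, or 23.0%; placebo 3 + 7.2 = 10.2, or 17.0%.

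The gap is 0.2w, that is 3 to 6 percentage points, although the risk is the same in each arm within each period.

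**The case against.** A reader might infer that the plan as a whole compares the arms' safety at different times. The documents do not support that.

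- The protocol synopsis (Safety Analyses) plans laboratory and vital-sign change from baseline without restricting it to End of Study. The protocol leaves detailed methods to the SAP, and SAP 11.5, 11.6 and 14.2 give change by visit or study time. A same-time comparison is therefore planned. This stands, and it confines the point to the protocol's End of Study change.
- No section says that Day 15 and Week 13 share one row. Protocol 7.2.1.7 calls Visit 6 the end of study for the Initial Treatment Period and takes laboratory samples and vital signs from every infant there, and Table 1 gives the two ends separate columns. On that reading, the change would be to Visit 6 for all and to Visit 9 for those who continue. Footnote b points the other way by assigning each infant one End of Study according to response. The pooled summary is thus the literal reading but not the only one, and the text should settle it.
- Protocol 8.4.4 makes all safety analysis descriptive, so no test or error rate is affected. This stands.
- The SAP was written to protocol V2.0 (30 October 2017), under which partial responders also continue to Week 13. Its two End of Study labels show that the term is ambiguous, but the 60%/40% mixture applies only to the current protocol.
- SAP 7.1 refers to table templates that are not in the supplied text, so a disposition layout split by period cannot be ruled out. Even so, neither text defines completion by period.

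A reader might also infer that an early CBD effect would be cut to 40% of its size in the CBD arm. That requires the effect to vanish by Day 90, although complete responders stay on assigned treatment. The documents give no basis for assuming so.

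**Conclusion.** The point holds in a limited form. Read literally, Protocol 8.4.4.2 and 8.4.4.3 with footnote b give a change summary whose timing depends on response. At the planning rates and before withdrawals it is centred on Day 60 in the CBD arm and Day 45 in the placebo arm, and it turns a shared drift d into an arm difference of 0.2d. The gap disappears if the response rates are equal, but the trial is designed on the expectation that they differ. The SAP's by-visit summaries already offer a like-for-like comparison, so the fault does not extend to the other laboratory and vital-sign summaries.

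The single disposition table has no such backup in the supplied text. Its distortion of 3 to 6 percentage points rests entirely on the assumed withdrawal risks, and its direction rests on more CBD than placebo infants entering the extension. Both faults are descriptive and leave the primary analysis untouched. They are worth correcting because safety and tolerability will be judged from descriptive tables.

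**What to change.** 1. **Protocol 8.4.4.2 and 8.4.4.3.** Replace the End of Study change with two named points: change to Visit 6 (Day 15) in all treated infants with a value, as the comparison between arms, and change to Visit 9 (Week 13) in infants who entered the extension. State that the second describes a group selected by response. Assign each Early Withdrawal value to the period in which it occurs.
2. **Protocol 8.4.1.1 and SAP 8.1.1.** Define completion for each period. Tabulate completion and withdrawal separately for the Initial Treatment Period (denominator: all randomised) and the Extended Treatment Period (denominator: complete responders who entered).
3. **SAP visit labels.** Align them with the current protocol. The SAP's Visit 5 is Day 14 with a blood draw, while the protocol draws at Visit 6 on Day 15; Week 13 is Visit 8 in the SAP and Visit 9 in the protocol. Give the two End of Study visits distinct names.

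The cost is some wording and a few more table columns. Laboratory tests and vital signs are already scheduled at both visits (Protocol 7.2.1.7 and 7.2.3), so no new data are needed.

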8.4.4.3. Vital Signs

For blood pressure, pulse rate, temperature, and respiration rate, descriptive statistics will be presented for values collected at Screening, Initial and Extended Treatment, End of Study /Early Withdrawal, and Follow-up Visits, and for the changes from baseline to End of Study /Early Withdrawal.

8.4.4.4. Neurological Examination Findings

Brief neurological examinations will be presented as the number and percentage of patients that have normal or abnormal results at Screening (complete exam), Initial and Extended Treatment, End of Study, Visit 6 and Visit 9 (complete exam), Early Withdrawal (complete exam), and Follow-up Visits.

8.4.5. Pharmacokinetic Analyses

Exploratory analyses of dose (exposure) will be performed. Further population PK approach may be used for PK parameter calculations, as appropriate.

8.4.6. Missing Data

There will be no imputation of the missing values. Patients without a video EEG assessment on Days 14-15 will be considered non-responders for all EEG-related endpoints. Percentage of spasm-free days will be calculated based on the number of entries (up to 15 days per measurement period). A sensitivity analysis may be conducted to assess the impact of the missing values on the final analysis. The sensitivity analyses will be detailed in the SAP.

9. STUDY CONDUCT

Steps to ensure the accuracy and reliability of data include the selection of qualified investigators and appropriate study sites, review of protocol procedures with the investigator and associated personnel prior to the study, periodic monitoring visits, and meticulous data management.

9.1. Sponsor and Investigator Responsibilities

9.1.1. Sponsor Responsibilities

The sponsor, and/or sponsor's representative is obligated to conduct the study in accordance with strict ethical and data privacy principles. The sponsor reserves the right to withdraw a patient from the study, to terminate participation of a study site at any time, and/or to discontinue the study.

The sponsor, or sponsor's representative, agrees to provide the investigator with sufficient material and support to permit the investigator to conduct the study according to the study protocol.

9.1.2. Investigator Responsibilities

By signing the Investigator's Agreement, the investigator indicates that she/he has carefully read the protocol, fully understands the requirements, and agrees to conduct the study in accordance with the procedures and requirements described in this protocol.

The investigator also agrees to conduct this study in accordance with all laws, regulations, and guidelines of the pertinent regulatory authorities, including and in accordance with the April 1996 International Conference on Harmonisation (ICH) Guidance for Industry E6 Good Clinical Practice (GCP) and in agreement with the 1996 Version of the Declaration of Helsinki. Furthermore, the investigator agrees to abide by the EU General Data Protection Regulations. While delegation of certain aspects of the study to sub-investigators and study coordinators is appropriate, the investigator will remain personally accountable for closely overseeing the study and for ensuring compliance with the protocol and all applicable regulations and guidelines. The investigator is responsible for maintaining a list of all persons that have been delegated study-related responsibilities (e.g., sub-investigators and study coordinators) and their specific study-related duties.

Investigators should ensure that all persons who have been delegated study-related responsibilities are adequately qualified and informed about the protocol, IPs, and their specific duties within the context of the study. Investigators are responsible for providing Insys with documentation of the qualifications, GCP training, and research experience for themselves and their staff as required by the sponsor and the relevant governing authorities.

To ensure compliance with the guidelines, the study will be audited by an independent person. The investigator agrees, by written consent to this protocol, to cooperate fully with compliance checks by allowing access to all study documentation by authorized individuals.

9.2. Site Initiation

Study personnel may not screen or enroll patients into the study until after receiving notification from the sponsor or sponsor's representative that the study can be initiated at the study site. The study site will not be authorized for study initiation until:

- The study site has received the appropriate institutional review board (IRB) approval for the protocol and the appropriate informed consent form.
- All regulatory documents have been submitted to and approved by the sponsor or sponsor's representative.
- The study site has a clinical trial agreement in place.

9.3. Screen Failures

Patients who fail inclusion and/or exclusion criteria may be re-screened based on prior investigator and Sponsor approval.

9.4. Study Documents

All documentation and material provided by the sponsor, or sponsor's representative for this study are to be retained in a secure location and treated as confidential material.

9.4.1. Investigator's Regulatory Documents

The regulatory documents must be received from the investigator and reviewed and approved by the sponsor or sponsor's representative before the study site can initiate the study and before the sponsor, or sponsor's representative, will authorize shipment of IP to the study site. Copies of the investigator's regulatory documents must be retained at the study site in a secure location.

Additional documents, including a copy of the protocol and applicable amendment(s), the IB, CRF/electronic case report form (eCRF) completion guidelines, copies of regulatory references, copies of IRB correspondence, and IP accountability records should also be retained as part of the investigator's regulatory documents. It is the investigator's responsibility to ensure that copies of all required regulatory documents are organized, current, and available for inspection.

9.4.2. Case Report Forms

By signing the Investigator's Agreement ([Section 13](#)), the investigator agrees to maintain accurate CRFs/eCRFs and source documentation as part of the case histories for all patients who sign an informed consent form (ICF).

Case report forms are considered confidential documents and should be handled and stored accordingly. The sponsor, or sponsor's representative, will provide the necessary training on the use of the specific CRFs/eCRF system used during the study to ensure that the study information is captured accurately and appropriately.

To ensure data accuracy, CRF/eCRF data for individual patient visits should be completed as soon as possible after the visit. All requested information must be entered in the CRF/electronic data capture (EDC) system according to the completion guidelines provided by the sponsor, or sponsor's representative.

9.4.3. Source Documents

All information recorded in the CRF/EDC system must be supported by corresponding source documentation. Examples of acceptable source documentation include, but are not limited to, hospital records, clinic and office charts, laboratory notes, and recorded data from automated instruments, memoranda, and pharmacy dispensing records.

During the study, select CRF/eCRF data may be used as original data collection tools as long as a description of this documentation process is maintained in the investigator's study files. Clinical laboratory data required by the protocol will be electronically transferred from the local laboratory to the sponsor or the sponsor's representative. A paper copy of the laboratory results will be provided to the study site and should be retained with each patient's source data.

All documents pertaining to the study, including a copy of the approved protocol, copy of the ICD, completed CRFs, source documents, drug accountability and retention records, and other study related documents will be retained in the permanent archives of the study site. These will be available for inspection at any time by the Sponsor or the FDA. Per 21 CFR 312, record retention for this study is required for a period of two years following the date on which this study agent is approved by the FDA for the marketing purposes that were the patient of this investigation; or, if no application is to be filed or if the application is not approved for such indication, until two years following the date on which the entire study is completed, terminated, or discontinued, and the FDA is notified.

The investigator will provide direct access to source data and documents for trial related monitoring, audits, IEC/IRB review, and regulatory requirements.

9.5. Data Quality Control

9.5.1. Monitoring Procedures

The investigator will permit the site monitor to review trial data as frequently as is deemed necessary to ensure data are being recorded in an adequate manner and protocol adherence is satisfactory. The investigator will access medical records for the monitor to verify CRF entries. The investigator, as part of his or her responsibilities, is expected to cooperate with the sponsor or its designee in ensuring the trial adheres to GCP requirements. The investigator may not recruit patients into the study until such time that a site visit has been conducted.

